10.2. Definitions of study populations

Intention-to-treat: The intention-to-treat population includes all study participants who have been randomised during the conduct of the study

Per-protocol: The per-protocol population includes all study participants who fulfill eligibility criteria specified in the inclusion/exclusion criteria (section 6.2 and 6.3), fitness criteria for randomisation (section 8) and received 7 days or less of appropriate antibiotics in the short arm, and 8 days or more of appropriate antibiotics in the long arm.

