Participants in the intervention (short duration) arm will receive antibiotics for up to 7 days. Antibiotics should be stopped from day 3 to 7 if respiratory cultures are negative and the patients fulfil a set of stringent clinical criteria signifying cardiopulmonary stability for 48 hours. If the respiratory cultures are positive, patients who fulfil the same set of clinical criteria should have their antibiotics stopped from day 5 to 7 (see section 8. Interventions). Antibiotics administered via all routes i.e. intravenous, oral and nebulisation should be stopped. Randomisation will be carried out when the participants fulfil the clinical stop criteria. The rationale for stopping antibiotics at the above time points is as follows:

Group 1: Short Duration arm

(a) Day 3

Patients who have negative respiratory cultures should have their antibiotics stopped from day 3 to 7 if the patient satisfies a set of criteria signifying clinical stability. As discussed above, though there are no randomised studies to support this, there are 2 observational studies [32, 33] showing that discontinuation of antibiotics in these cases did not result in a higher mortality or rate of new respiratory infections compared to those whose antibiotics were continued. In addition, those whose antibiotics were withheld had a lower rate of total secondary infections by MDROs. One of these studies concluded that antibiotics could be safely discontinued in patients with negative respiratory cultures with no significant impact on mortality, despite persistence of signs and symptoms of pneumonia in 35% of these patients [32]. The above studies have led to the recommendation in the 2016 IDSA/ATS guideline that for patients with suspected VAP whose respiratory invasive culture results are below the diagnostic threshold for VAP, antibiotics should be withheld rather than continued [3].

(b) Day 5-7

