This is a non-inferiority trial with a hierarchical noninferiority–superiority hypothesis. The first analysis to be conducted will be for determination of non-inferiority. Only if non-inferiority is established by this primary analysis, a second analysis for superiority will be conducted using closed testing methods without requiring adjustment of the significance level for multiple comparisons. [39] The trial estimates for the primary outcome will be calculated with the absolute risk difference (proportion of participants with the primary outcome in the short arm minus that in the long arm). Hence, non-inferiority will be concluded if the upper boundaries of the one-sided 95% confidence intervals from both unadjusted and adjusted analyses are below the non-inferiority margin. The purpose of using both adjusted analyses on the intention-to-treat and per-protocol populations to determine non-inferiority is to minimise the inflation of type 1 error associated with non-adherence in non-inferiority trials. [40] Superiority will be declared if the entire confidence intervals for all the trial estimates are above zero.

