2.6. Hypotheses and Definition of Primary and Secondary Outcomes

Primary end point

The primary end point of the study is the difference in the proportion of participants with the composite endpoint of death and VAP recurrence rate within 60(± 5) days of enrolment.

Death refers to all-cause mortality. VAP recurrences are episodes which satisfy the US CDC VAP criteria, and verified by two independent respiratory or infectious diseases physicians blinded to the randomisation arm.

The first statistical test for the primary end point will be for non-inferiority. Here, the null hypothesis (H_0): $\theta \geq \delta$ will be tested against the alternative (H_1): $\theta < \delta$, where θ is the treatment effect difference between the proportion of participants who have the primary outcome in the short and long treatment strategy groups, and δ is the fixed non-inferiority margin of 12%.

In the event that short is non-inferior to the long treatment strategy, standard two-sided superiority testing will be performed. That is, the null hypothesis (H_0): $\theta = 0$ will be tested against the alternative (H_1): $\theta > 0$, where θ is the treatment effect difference between the proportion of participants who have the primary outcome in the short and long treatment strategy groups.

Secondary end points

All statistical tests for the secondary endpoints are standard two-sided superiority tests.

a) Ventilator-associated events

Definition: Events which satisfy the US CDC VAP criteria ¹ but were not verified by two independent respiratory or infectious diseases physicians.

H_0 : There is no difference in the proportion of participants who have ventilator-associated events in the short and long treatment strategy groups, i.e. $\theta^{VAE} = 0$;

H_1 : There is a difference in the proportion of participants who have ventilator-associated events in the short and long treatment strategy groups, i.e. $\theta^{VAE} \neq 0$;

where θ^{VAE} is the treatment effect difference between the proportion of participants in the short and long treatment strategy groups.

b) Duration of mechanical ventilation

Definition: Total duration of mechanical ventilation during the 60 days of follow-up after enrolment.

H_0 : There is no difference in the total duration of mechanical ventilation in the short and long treatment strategy groups, i.e. $t^v_s = t^v_l$;

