5.5. Description of Adherence with Intervention

Adherence with randomised intervention will be carefully assessed since poor adherence may increase type 1 error.

Adherence in the short arm is defined as all antibiotics being stopped 7 days or fewer from the start date of appropriate antibiotics or VAP respiratory symptom onset date, whichever is later. For example, for a participant who started having respiratory symptoms on 1st March 2020, and who was prescribed an appropriate antibiotic (e.g. meropenem) on 2nd March 2020, day 0 for which antibiotic duration is based on is 2nd March 2020. This participant will be considered adherent if all antibiotics (other than, when applicable, anti-tuberculosis antibiotics, prophylaxis e.g. peri or post operative or in immunocompromised hosts, gut prokinetic antibiotics) are stopped by 9th March 2020. Antibiotics are allowed to

be restarted subsequently for clinical indications. The percentage of participants in the short arm for whom antibiotics are restarted will be reported in the final report.

Adherence in the long arm is defined as antibiotics being continued for more than 7 days from the start date of appropriate antibiotics or VAP respiratory symptom onset date, whichever is later. For example, the same participant who started having respiratory symptoms on 1st March 2020, and who was prescribed an appropriate antibiotic (e.g. meropenem) on 2nd March 2020, day 0 for which antibiotic duration is based on is 2nd March 2020. This participant will be considered adherent if any antibiotics (other than, when applicable, anti-tuberculosis antibiotics, prophylaxis e.g. peri or post operative or in immunocompromised hosts, gut prokinetic antibiotics) are continued on or after 10th March 2020.

Antibiotic durations for the index episode of VAP, calculated using the above descriptions, will be presented in a survival plot to show the distribution of the data. This demonstrates how successful the trial intervention is and no statistical analysis will be performed. Total antibiotic duration, classified by short and long arms, during 60-day follow-up will be analysed as a secondary outcome.

The proportion of participants who are non-adherent will be presented in the CONSORT diagram with a breakdown of the actual reasons.

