6. PATIENT GROUPS FOR ANALYSIS

The following patient populations will be utilised in the analysis:

Intention-to-treat (ITT)

The intention-to-treat population includes all study participants who have been randomised during the conduct of the study

Per-protocol

The per-protocol population includes all study participants who fulfill eligibility criteria specified in the inclusion/exclusion criteria, fitness criteria for randomisation and who received 7 days or fewer of appropriate antibiotics in the short arm, and 8 days or more of appropriate antibiotics in the long arm (Section 5.5).

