7.2. Statistical Methods Used for Analysis of Primary Outcome

Based on both the ITT and PP population, the proportions of participants experiencing the primary endpoint will be tabulated by treatment group. If the absolute, upper two-sided 90% CIs around the absolute unadjusted difference is less than 12%, then the criteria of non-inferiority will be met.

A multivariable logistic regression model, will be applied on the ITT population to calculate the estimates of the treatment differences adjusted for baseline patient characteristics described above. Categories with low counts may be combined. For example, in the event of comorbidities with very low counts, these comorbidities may be combined to avoid difficulties with the maximum likelihood estimation of the logistic model. Where no

information has been entered on the comorbidities, the participants will be considered not to suffer from these comorbidities.

For the PP population, inverse probability weighting⁹ will be applied to calculate the estimates of the treatment differences using the same baseline patient characteristics as above.

For these multivariate logistic regression models, residual and predicted values produced from the model will be examined to assess the assumptions of the model. Specifically, the assumption of linearity between the predicted log odds and the covariates is assessed by plotting lowess graphs. The independence of the error terms will be considered. Influential cases are investigated by plotting the standardised Pearson's residuals against the predicted probabilities and the leverage of the individual observations.

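### The per-protocol rule has no exception for death, so an early long-arm death leaves the per-protocol population while a short-arm death on the same day stays; the effect is probably small

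*Protocol*

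**What the plan says.** Protocol 10.2 defines PP by eligibility, the fitness criteria and antibiotic days: participants must have "received 7 days or less of appropriate antibiotics in the short arm, and 8 days or more of appropriate antibiotics in the long arm". SAP 6 uses the same cut and refers to SAP 5.5, where "Adherence in the long arm is defined as antibiotics being continued for more than 7 days from the start date of appropriate antibiotics" or from symptom onset, whichever is later. SAP 5.5 exempts certain kinds of antibiotic (anti-tuberculosis, prophylactic, prokinetic). It does not mention death. It also promises that "The proportion of participants who are non-adherent will be presented in the CONSORT diagram with a breakdown of the actual reasons".

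Four other provisions matter.

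- **Timing.** Under Protocol section 5, "Randomisation will be carried out when the participants fulfil the clinical stop criteria". Protocol section 8 places this on days 3 to 7, or days 5 to 7 if a respiratory culture is positive.
- **Endpoint.** SAP 2.6 counts death in the primary composite: "Death refers to all-cause mortality".
- **Adjustment.** For PP, SAP 7.2 says that inverse probability weighting "will be applied to calculate the estimates of the treatment differences using the same baseline patient characteristics as above".
- **Role of PP.** Protocol 10.1 refers to "The purpose of using both adjusted analyses on the intention-to-treat and per-protocol populations to determine non-inferiority", as a guard against type I error inflation from non-adherence. SAP 7.7 treats ITT and PP as parts of the primary analysis and plans no further sensitivity analysis for it.

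**The concern.** A long-arm participant who dies after randomisation and before day 8 cannot reach 8 days of antibiotics, even if every instruction was followed. The rule removes that participant, and with them an event, from the long arm. A short-arm participant who dies on the same day has had 7 days or fewer and stays, with the event counted. PP membership is therefore conditioned on the primary outcome in one arm only. Baseline covariates cannot restore people who were removed because of the outcome itself.

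What is at stake is the PP half of the non-inferiority decision. Removing only long-arm events lowers the long-arm rate and raises short minus long, so PP could fail when ITT passes. The CONSORT breakdown should make the deaths visible, but the PP estimate would still be computed without them.

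**Working it through.** **Inputs from the documents.** Event rate 55%, margin 12 points, one-sided alpha 5%, power 80%, maximum 412 patients and 460 enrolled (Protocol section on the number of participants; SAP 2.5). Allocation is 1:1, so 206 per arm before the loss allowance and 230 per arm as the SAP 2.2 target. All-cause mortality in VAP is 20-50% (Protocol section 3). Randomisation on days 3 to 7 leaves 1 to 5 days before day 8, or 1 to 3 days for culture-positive patients.

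**Assumptions.** The documents do not give d, the share of the long arm dying in this window. I use 20-50% as 60-day mortality with a constant hazard. I use the all-cause range because the endpoint is all-cause death; the 13.6-42.8% in the sample-size section is attributable mortality.

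**The plan's own figure.** With unpooled variance, n per arm = (1.645 + 0.842)² × (2 × 0.55 × 0.45) / 0.12² = 212.5, so 213 per arm and 426 in total. With the variance taken at 55% versus 67%, n = 201.2, so 202 per arm and 404 in total. The stated 412 lies between the two. At 206 per arm the unpooled power is Φ(0.12/0.04902 − 1.645) = 78.9%; at 230 per arm it is 82.7%. The loss allowance gives 412/0.9 = 458, in line with 460. The sample size is not in dispute.

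**Effect of the rule.** With true rates equal at 55%:

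- d = 1 − (1 − m)^(w/60), for mortality m and window w in days
- long-arm PP rate = (0.55 − d)/(1 − d)
- shift in short minus long = 0.55 − (0.55 − d)/(1 − d) = 0.45 × d/(1 − d)
- PP power = Φ((0.12 − shift)/SE − 1.645), with unpooled SE and a long arm of N(1 − d)

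For example, m = 20% and w = 5 gives d = 1 − 0.8^(5/60) = 1.84%. The long-arm PP rate is (0.55 − 0.0184)/(1 − 0.0184) = 54.16%, a shift of +0.84 points.

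| m | w (days) | d | Deaths of 206 | Shift (points) | Power, 206/arm | Power, 230/arm |
|---|---|---|---|---|---|---|
| none excluded | – | 0 | 0 | 0 | 79% | 83% |
| 20% | 1 | 0.37% | 0.8 | +0.17 | 78% | 82% |
| 20% | 3 | 1.11% | 2.3 | +0.50 | 76% | 80% |
| 20% | 5 | 1.84% | 3.8 | +0.84 | 73% | 77% |
| 50% | 1 | 1.15% | 2.4 | +0.52 | 75% | 79% |
| 50% | 3 | 3.41% | 7.0 | +1.59 | 68% | 72% |
| 50% | 5 | 5.61% | 11.6 | +2.68 | 59% | 63% |

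**False non-inferiority.** With a true difference of 12 points (67% versus 55%) and 206 per arm, the same formula gives a PP-alone type I error of 5.0% with no exclusion, 4.7% in the 20%, 1-day row and 1.4% in the 50%, 5-day row. This mechanism makes PP stricter.

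**Sensitivity to constant hazard.** If deaths in the window were 2.5 times as frequent as an even spread (assumed), d would run from 0.20/60 × 1 × 2.5 = 0.83% to 0.50/60 × 5 × 2.5 = 10.4%. The shift would run from 0.45 × 0.0083/0.9917 = +0.4 to 0.45 × 0.104/0.896 = +5.2 points. Randomising only stable patients argues against such front-loading.

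**The case against.** The strongest reply is that this is a small matter in a safe direction. Patients are randomised once stable, SOFA above 11 is excluded, and culture-positive patients have at most three days at risk. ITT keeps everyone, and the mechanism makes PP stricter. PP is also there to guard against inflation from non-adherence, and keeping these deaths moves it towards ITT. All of this stands and limits the severity. It does not justify a rule that selects on the endpoint in one arm, particularly as a sentence would remove it.

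Two stronger readings are tempting, and the documents support neither.

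- A reader might infer that PP as a whole is biased against the short arm. The same rule also removes long-arm participants stopped before day 8, who may have done well, and that would push the other way. The documents give neither the size nor the event risk of that group, so the net direction is unknown.
- A reader might infer a substantial offset from short-arm participants continued past day 7 under the treatment-failure or new-infection exception in Protocol section 8. That group should be small. SAP 2.7 has short-arm antibiotics stopped on the day of randomisation, and SAP 5.5 treats later restarts for clinical indications as compatible with adherence. These passages need to be reconciled with section 8, but no offset can be computed from them.

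**Conclusion.** The asymmetry is in the text of both documents, and no section provides an exception. Taken alone it raises the PP risk difference by 0.45 × d/(1 − d). That is about +0.2 to +2.7 points for d between 0.4% and 5.6%, with PP power of 78% to 59% against 79% at 206 per arm. The low end is more plausible. The range rests on a borrowed mortality figure, a constant hazard and an assumed window, so small is likely but not assured.

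A reader might also infer that the rule could produce a false claim of non-inferiority. If ITT and PP must both pass, as Protocol 10.1 suggests, it cannot: it only makes PP harder to pass. The practical risk is PP failing while ITT passes, for a reason that has nothing to do with adherence. Severity: minor.

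**What to change.** In Protocol 10.2 and SAP 5.5 and 6, add: *A participant in either arm who dies before day 8, and whose antibiotics had not departed from the assigned strategy before death, counts as adherent and stays in the per-protocol population.* Report the number affected, by arm, in the CONSORT breakdown already planned in SAP 5.5.

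I would not add a sensitivity analysis that also readmits long-arm participants stopped before day 8. It would keep nearly all long-arm non-adherers while still removing some short-arm deviators, which is a new one-arm asymmetry. Nor should the rule depend on judging whether a stop was linked to the terminal event, since the antibiotic dates largely reveal the arm.

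The cost is one sentence in each definition and two counts. The dates and deaths are already in the 100% data-entry check (SAP 3). The downside is that PP moves slightly closer to ITT and loses a small conservative component. Timing matters more: follow-up ended on 14 February 2023 (SAP 2.2) and the trial statistician is not blinded (SAP 9.2). The rule should be fixed with the monitoring committee's approval, which SAP 4 requires for amendments, before PP results are seen. Otherwise it should be reported as a deviation.

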10.3. Interim analyses

Four interim analyses will be performed on the primary endpoint whenever 25% of patients has been randomised and have completed the 60 (± 5) days follow-up. The interim analyses will be performed by a trial statistician in coordination with the study team. The statistician will report to the independent data and Data and Safety Monitoring Committee (DSMC). The DSMC will have unblinded access to all data and will discuss the results of the interim-analysis during a DSMC meeting. A trial steering committee will also be constituted and will decide on the continuation of the trial and will report to the central ethics committee. The trial will be terminated if superiority of either short or long treatment durations is shown. We will use the group sequential design adopting the boundaries proposed by Fleming- Harrington- O'Brien ($R=0.8$) [41] to terminate the trial prematurely once the Z value exceeds the defined boundaries for superiority.

10.2. The Number of Participants

The study is designed to demonstrate the non-inferiority, followed by superiority, on the composite endpoint of mortality and recurrence at 60(± 5) days of the short duration versus the long duration of antibiotic treatment for VAP. A meta-analysis showed that mortality attributable to VAP ranges from 13.6–42.8% in Southeast Asia [42]. Considering that our primary outcome is a composite binary outcome of mortality and recurrence of VAP, we estimate this to be 55%. We derived an absolute non-inferiority margin of 12% with the fixed-margin method, preserving at least 50% of the efficacy of standard treatment in VAP. Using a group sequential design adopting the boundaries proposed by Fleming- Harrington- O'Brien ($R=0.8$) [40], a maximum of 412 patients will be required to achieve a power of 80% to conclude non-inferiority between the two groups with an one-sided α risk of 5%. As we anticipate a loss to follow-up of up to 10%, we plan to enrol a maximum of 460 patients.

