2.5. Non-inferiority margin and sample size

The study is designed as a hierarchical non-inferiority /superiority trial where, if non-inferiority can be established, superiority will be assessed. The primary outcome is the composite endpoint of mortality and recurrence at 60(± 5) days of the short duration versus

the long duration of antibiotic treatment for VAP. A meta-analysis showed that mortality attributable to VAP ranges from 13.6 to 42.8% in Southeast Asia⁴. Considering that our primary outcome is a composite binary outcome of mortality and recurrence of VAP, we estimate this to be 55%. We derived an absolute non-inferiority margin of 12% with the fixed-margin method, preserving at least 50% of the efficacy of standard treatment in VAP. Using a group sequential design adopting the boundaries proposed by Fleming- Harrington- O'Brien ($R=0.8$)⁵, a maximum of 412 patients will be required to achieve a power of 80% to conclude non-inferiority between the two groups with an one-sided α risk of 5%. As we anticipate a loss to follow-up of up to 10%, we plan to enrol a maximum of 460 patients.

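### The stated 80% power belongs to one unadjusted comparison in 412 patients; the plan concludes from both ITT and per-protocol results, and the lower power of that joint rule is not given

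*Protocol*

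**What the plan says.** **Sample size.** Protocol 10.2 (The Number of Participants) assumes a composite event rate of 55% and a one-sided 5% level. On the margin it says "We derived an absolute non-inferiority margin of 12% with the fixed-margin method". It concludes that "a maximum of 412 patients will be required to achieve a power of 80% to conclude non-inferiority between the two groups", and then: "As we anticipate a loss to follow-up of up to 10%, we plan to enrol a maximum of 460 patients". SAP 2.5 gives the same figures. Neither section mentions per-protocol exclusions or more than one criterion.

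**Decision rule, protocol.** Protocol 10.1 concludes non-inferiority if the "upper boundaries of the one-sided 95% confidence intervals from both unadjusted and adjusted analyses are below the non-inferiority margin". It adds that adjusted analyses in both the ITT and the PP population serve to determine non-inferiority.

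**Decision rule, SAP.** SAP 7.2 opens: "Based on both the ITT and PP population, the proportions of participants experiencing the primary endpoint will be tabulated by treatment group". Its criterion is that the upper limit of the two-sided 90% interval for the unadjusted difference is below 12%. SAP 7.7 describes the ITT and PP analyses as parts of the primary analysis.

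**Populations.** ITT is everyone randomised (Protocol 10.2, Definitions of study populations; SAP 6). SAP 7.1 keeps participants with incomplete follow-up and no observed event in the analysis as non-events. PP requires eligibility, fitness for randomisation, and at most 7 days of appropriate antibiotics in the short arm or at least 8 in the long arm. No expected PP fraction is given.

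**The concern.** A power figure should belong to the rule by which the trial will be judged. Here the 80% is described as the chance of concluding non-inferiority, but it was computed for one confidence limit in one set of 412 patients. If the ITT and PP limits must both fall below 12%, the chance of success cannot exceed that of either limit alone, and the PP limit is wider because its set is smaller. Requiring adjusted limits as well can only lower the chance further.

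What is at stake is how a miss is read. Suppose ITT passes and PP narrowly fails. A reader who takes 80% as the power of the whole rule may see that as evidence against the short course, when part of the explanation is the smaller PP set.

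**Working it through.** **Inputs.** From Protocol 10.2 (The Number of Participants): event rate 0.55 in both arms (true difference 0), margin 0.12, one-sided 5% (z = 1.645), 412 in total. Allocation is 1:1 (Protocol 7.4), so 206 per arm. The PP fraction f is not in the documents; the range 70-95% of ITT is an assumption.

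**Step 1: reproduce the plan's figure.**
- SE = sqrt(2 × 0.55 × 0.45 / 206) = 0.0490.
- Power = Φ(0.12/0.0490 − 1.645) = Φ(0.803) = 78.9%. Simulating the Wald limit (200,000 trials) gives about 80%.
- Run the other way, the formula gives 213 per arm, or 426, for 80% power at a 55% event rate, before any group sequential inflation. That is 3.4% above 412.

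The 80% is thus recovered, to within about one point, as the power of one unadjusted comparison. Nothing is left over for a second criterion.

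**Step 2: the inflation.** 412/0.9 = 457.8, hence 460. The 10% loss to follow-up accounts for all of it. With all 460 analysed, SE = sqrt(0.495/230) = 0.0464, and single-comparison power is Φ(0.12/0.0464 − 1.645) = 82.7%.

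**Step 3: ITT and PP unadjusted limits together.** Treat PP as a random fraction f of ITT. Then SE(PP) = SE(ITT)/sqrt(f), and the two estimates have correlation sqrt(f). Joint power is the bivariate normal probability that both upper limits are below 0.12. For example, at f = 0.90 and N = 412, SE(PP) = 0.0490/sqrt(0.9) = 0.0517; PP alone passes with probability 75.1%, and both pass with probability 72.8%.

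| PP as share of ITT | PP alone, ITT 412 | Both limits, ITT 412 | Both limits, ITT 460 |
|---|---|---|---|
| 95% | 77.1% | 75.2% | 79.4% |
| 90% | 75.1% | 72.8% | 77.1% |
| 85% | 73.0% | 70.5% | 74.9% |
| 80% | 70.7% | 68.1% | 72.5% |
| 75% | 68.3% | 65.5% | 70.1% |
| 70% | 65.7% | 62.9% | 67.5% |

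Binomial simulation (200,000 trials per setting) agrees to about one point: 73.3% and 68.1% for 412 at 10% and 20% excluded, and 78.0% and 73.1% for 460. With 460 and 5% excluded it gives 80.3%.

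**Step 4: adjusted limits as well.** A smaller simulation (3,000 trials) required all four limits: ITT unadjusted, ITT adjusted, PP unadjusted, PP weighted. For f = 95%, 90% and 80% it gave about 72%, 69% and 64% with 412, and 76%, 73% and 68% with 460. It used assumed covariates, and a linear model in place of the planned logistic model for ITT. It shows the direction and rough size only.

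**The case against.** Four points deserve weight.

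- **The size is not a fact of the documents.** A reader might infer that the power of the design is about 65-73%. That needs 412 in ITT and a PP fraction of about 74-90%, and the documents give neither as the analysis set. SAP 6 and 7.1 keep lost participants in the ITT denominator, so ITT may approach 460. There, with few exclusions, the joint rule roughly reaches the stated 80%. This objection stands, and it is why the result is given as a conditional range.
- **The rule itself is unsettled.** A reader might also infer that SAP 7.2 explicitly requires both limits to pass. It does not say so: its opening sentence concerns tabulation, and its criterion names only the unadjusted difference. The joint reading comes from that section together with SAP 7.7 and Protocol 10.1, and Protocol 10.1 does not list every population-by-analysis limit either. This stands, and makes reconciliation the first step.
- **The plan tries to limit PP losses.** Randomisation waits for the fitness criteria (Protocol 7.4), physicians are contacted beforehand (12.2), and discontinued participants are replaced (7.8). These measures may keep f high. But replacement aims at the calculated sample size, not at a PP size. Protocol section 8 keeps short-arm deviations in ITT, and also lets some short-arm patients continue beyond day 7, who can then fall outside PP.
- **There is no slip in the arithmetic.** Agreed: 412 is about right for the comparison it describes. The fault is that this comparison is not the plan's rule.

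**Conclusion.** The point holds in conditional form. The 80% in Protocol 10.2 and SAP 2.5 is the power of one unadjusted comparison in 412 patients. The plan bases its conclusion on ITT and PP together and, in the protocol, on adjusted as well as unadjusted limits. That the joint rule has lower power than a single comparison at the same ITT size needs no assumed adherence rate, only a PP set that differs from ITT.

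The size does need assumptions: PP at 70-95% of ITT, exclusions unrelated to outcome, no true difference, and interim looks ignored. On these, two-limit power is about 63-75% with 412 in ITT (73% at 10% excluded, 68% at 20%). With 460 it is about 67-79% (77% at 10%, 72-73% at 20%). It is lower if the adjusted limits must also pass. The documents do not support a single figure for the power of the trial, nor the conclusion that more patients had to be recruited.

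**What to change.** 1. Reconcile Protocol 10.1 and SAP 7.2 so that one sentence, identical in both, lists which population-by-analysis limits must fall below 12%.
2. In Protocol 10.2 (The Number of Participants) and SAP 2.5, state that 80% refers to one unadjusted comparison in 412 patients.
3. In the same places, add a table of the power of the agreed rule by assumed PP fraction, for ITT sizes of 412 and 460, with its assumptions. The table above serves if the rule is the two unadjusted limits. If adjusted limits are included, rerun it with the planned models.

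The cost is wording in four sections and one short table. No extra patients are needed and the margin does not change; SAP 2.2 gives recruitment as ended on 16 December 2022. The downside is a less favourable stated power.
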